## 7. ADVERSE EVENTS

The following list of adverse events (Section 7.1, Appendices B and C) and the characteristics of the observed AEs (Section 7.2) will determine whether the event requires expedited reporting via the MedWatch Forms **in addition** to routine reporting.

### 7.1 Expected Toxicities and Supportive Care guidelines

**Adverse Event List for rucaparib:** nausea, fatigue (including asthenia), vomiting, anemia, dysgeusia, AST/ALT elevation, constipation, decreased appetite, diarrhea, thrombocytopenia, neutropenia, stomatitis, nasopharyngitis/URI, rash, abdominal pain/distention, and dyspnea. Myelodysplastic Syndrome/Acute Myeloid Leukemia (MDS/AML) and Embryo-Fetal Toxicity. See also Appendix B.

**Adverse Event List for nivolumab:** Fatigue, rash, musculoskeletal pain, pruritus, diarrhea, nausea, asthenia, cough, dyspnea, constipation, decreased appetite, back pain, arthralgia, upper respiratory tract infection, pyrexia, headache, abdominal pain, and vomiting. Immune-mediated pneumonitis, Immune-mediated colitis, Immune-mediated hepatitis, Immune-mediated endocrinopathies, Immune-mediated nephritis and renal dysfunction, Immune-mediated skin adverse reactions, Immune-mediated encephalitis, Infusion reactions. See also Appendix C.

#### 7.1.1 Supportive care guideline for rucaparib and nivolumab toxicity

**Opportunistic Infections:** It is rare for a patient receiving immunosuppression for nivolumab-related AEs to develop an opportunistic infection. Subjects with inflammatory events of any organ category expected to require more than 4 weeks of corticosteroid or other immunosuppressive agents to manage the AE should be considered for antimicrobial/antifungal prophylaxis, per institutional guidelines, to prevent opportunistic infections such as *P. jiroveci* (formerly *P. carinii*) and fungal infections.

**Immune-Mediated Pneumonitis:** Nivolumab can cause immune-mediated pneumonitis, defined as requiring use of corticosteroids and no clear alternate etiology. Fatal cases have been reported. Monitor patients for signs with radiographic imaging and for symptoms of pneumonitis. Administer corticosteroids at a dose of 1 to 2 mg/kg/day prednisone equivalents for moderate (Grade 2) or more severe (Grade 3-4) pneumonitis, followed by corticosteroid taper. Please refer to section 6 for dose modification guidance.

**Immune-Mediated Colitis:** Nivolumab can cause immune-mediated colitis, defined as requiring use of corticosteroids with no clear alternate etiology. Monitor patients for signs and symptoms of colitis. Administer corticosteroids at a dose of 1 to 2 mg/kg/day prednisone equivalents followed by corticosteroid

taper for severe (Grade 3) or life-threatening (Grade 4) colitis. Administer corticosteroids at a dose of 0.5 to 1 mg/kg/day prednisone equivalents followed by corticosteroid taper for moderate (Grade 2) colitis of more than 5 days duration; if worsening or no improvement occurs despite initiation of corticosteroids, increase dose to 1 to 2 mg/kg/day prednisone equivalents. Refer to section 6 for dose modification guidance.

**Immune-Mediated Hepatitis:** Nivolumab can cause immune-mediated hepatitis, defined as requiring use of corticosteroids and no clear alternate etiology. Monitor patients for abnormal liver tests prior to and periodically during treatment. Administer corticosteroids at a dose of 1 to 2 mg/kg/day prednisone equivalents followed by corticosteroid taper for severe (Grade 3) or life-threatening (Grade 4) transaminase elevations, with or without concomitant elevation in total bilirubin. Administer corticosteroids at a dose of 0.5 to 1 mg/kg/day prednisone equivalents for moderate (Grade 2) transaminase elevations. Refer to section 6 for dose modification guidance.

**Immune-Mediated Endocrinopathies:** Nivolumab can cause immune-mediated hypophysitis. Monitor patients for signs and symptoms of hypophysitis. Administer hormone replacement as clinically indicated and corticosteroids at a dose of 1 mg/kg/day prednisone equivalents followed by corticosteroid taper for moderate (Grade 2) or greater hypophysitis. Refer to section 6 for dose modification guidance.

**Adrenal Insufficiency:** Nivolumab can cause immune-mediated adrenal insufficiency. Monitor patients for signs and symptoms of adrenal insufficiency. Administer corticosteroids at a dose of 1 to 2 mg/kg/day prednisone equivalents followed by a corticosteroid taper for severe (Grade 3) or life-threatening (Grade 4) adrenal insufficiency. Please refer to section 6 for dose modification guidance.

**Immune-Mediated Nephritis and Renal Dysfunction:** Nivolumab can cause immune-mediated nephritis, defined as renal dysfunction or Grade 2 increased creatinine, requirement for corticosteroids, and no clear alternate etiology. Monitor patients for elevated serum creatinine prior to and periodically during treatment. Administer corticosteroids at a dose of 1 to 2 mg/kg/day prednisone equivalents followed by corticosteroid taper for life-threatening (Grade 4) increased serum creatinine. Administer corticosteroids at a dose of 0.5 to 1 mg/kg/day prednisone equivalents for moderate (Grade 2) or severe (Grade 3) increased serum creatinine, if worsening or no improvement occurs, increase dose of corticosteroids to 1 to 2 mg/kg/day prednisone equivalents. Please refer to section 6.

**Immune-Mediated Encephalitis:** Nivolumab can cause immune-mediated encephalitis with no clear alternate etiology. Evaluation of patients with neurologic symptoms may include, but not be limited to, consultation with a neurologist, brain MRI, and lumbar puncture.

Withhold OPDIVO in patients with new-onset moderate to severe neurologic signs or symptoms and evaluate to rule out infectious or other causes of moderate to severe neurologic deterioration. If other etiologies are ruled out, administer corticosteroids at a dose of 1 to 2 mg/kg/day prednisone equivalents for patients with immune-mediated encephalitis, followed by corticosteroid taper. Permanently discontinue OPDIVO for immune-mediated encephalitis

**Infusion Reactions:** Nivolumab can cause severe infusion reactions, which have been reported in less than 1.0% of patients in clinical trials. Discontinue OPDIVO in patients with severe or life-threatening infusion reactions. Interrupt or slow the rate of infusion in patients with mild or moderate infusion reactions

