## 5.2 Nivolumab and Rucaparib Administration

The recommended starting dose of rucaparib as a continuously administered oral monotherapy is 600 mg BID. Patients may take rucaparib with or without food. Each dose should be taken with approximately 8 oz. (240 mL) of room temperature water. Tablets should be swallowed whole without crushing or chewing. Patients should take rucaparib doses as close as possible to 12 hours apart, preferably at the same time every day. If a patient misses a dose (i.e., does not take it within 4 hours of the scheduled time), the patient should skip the missed dose and resume by taking the next scheduled rucaparib dose. Missed or vomited doses should not be made up.

Modification of rucaparib dose may be a necessary component of AE management, and study-specific protocol guidelines for dose modifications should be followed. See Section 6.

Nivolumab will be administered as intravenous infusion once every 4 weeks at fixed dose of 480 mg. The FDA has approved a supplemental biologics license application adding a 4-week dosing schedule for nivolumab (Opdivo) across several of the PD-1 inhibitor's indications (non-small cell lung cancer, renal cell carcinoma, metastatic urothelial carcinoma, Hodgkin lymphoma, metastatic squamous cell carcinoma and hepatocellular carcinoma). Adding a q 4 weekly regimen will be convenient for patients and will be more cost effective as it will reduce number of visits to infusion center. We have had no problem with using q4 week dosing in SCLC at our center. No dose modification will be allowed (other than hold or discontinue). Please refer to Section 6 for guidance regarding Nivolumab schedule in response to toxicity.

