## 6. DOSING DELAYS/DOSE MODIFICATIONS

Doses of oral study drug (rucaparib), and/or IV study drug (nivolumab), may be interrupted or delayed for toxicity and other protocol-specified criteria. **Dose reductions are permitted for Rucaparib, but not for Nivolumab.** The assessment for delay or discontinuation should be made separately for the oral study drug (rucaparib) and the IV study drug (nivolumab) where class-specific safety profiles do not overlap; however, if toxicity is considered related to all study drugs or if the investigator is unable to determine which study drug is the cause of the AE, then all study drugs in the combination should be delayed and/or discontinued. For management of AEs which can be clearly attributed to rucaparib OR nivolumab, independent dose modification for either agent is allowed. If the relationship to an AE that is common to both drugs can be clearly distinguished, then a recommendation from the ET CCART for continuation of the non-offending drug can be requested by the investigator. Treatment may be prematurely discontinued due to withdrawal of consent, unacceptable toxicity, disease progression, completion of treatment cycles, or termination of the study, whichever occurs first.

Dose modification and re-treatment of oral and/or IV study drug are to be based on criteria presented in Table 4.

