**Table 4. Dose Modification and Re-treatment Criteria for Oral and IV Study Drugs**

| Adverse Event  | Severity (CTCAE Grade) | Oral Study Drug (rucaparib)    |                        | IV Study Drug (nivolumab)      |                                    |
|--|------------------------|--------------------------------|------------------------|--------------------------------|------------------------------------|
|  |                        | Dose Modification  | Re-treatment           | Dose Modification  | Re-treatment                       |
| Non-hematological Non-skin AEs  |                        |                                |                        |                                |                                    |
| Adverse event, except fatigue  | 2                      | None                           | N/A                    | Hold                           | Grade ≤ 1 or baseline  |
| Any adverse event (related events lasting > 7 days for nivolumab, exceptions below)  | 3 or 4                 | Hold                           | ≤ Grade 2  | Discontinue                    |                                    |
| Exceptions with rucaparib   |                        |                                |                        |                                |                                    |
| Nausea, Vomiting, Diarrhea adequately controlled with systemic antiemetics/antidiarrheal medications lasting <7 days.  | 3               | None                           |                        |                                |                                    |
| ALT/AST provided no signs of liver dysfunction (see laboratory section below)  | 3                      | None                           |                        |                                |                                    |
| Exceptions with nivolumab   |                        |                                |                        |                                |                                    |
| Uveitis, pneumonitis, bronchospasm, neurological toxicity, hypersensitivity reaction or infusion reaction of any duration                                      | 3                      |                                |                        | Discontinue                    |                                    |

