**Table 4. Dose Modification and Re-treatment Criteria for Oral and IV Study Drugs**

| Adverse Event  | Severity (CTCAE Grade)              | Oral Study Drug (rucaparib)    |                      | IV Study Drug (nivolumab)      |                                    |
|--|-------------------------------------|--------------------------------|----------------------|--------------------------------|------------------------------------|
|  |                                     | Dose Modification  | Re-treatment         | Dose Modification  | Re-treatment                       |
| ALT or AST > 3 × ULN AND bilirubin > 2 × ULN (suspected DILI)  |                                     | Hold               |                      | Discontinue                    |                                    |
| Creatinine elevations  | 2 (≥ 1.5 x baseline  ) | None                           | N/A                  | Hold                           | Grade ≤ 1 or baseline  |
| Creatinine elevations  | 3                                   | Hold                           | Grade 2  | Hold                           | Grade ≤ 1 or baseline  |
| Exception with nivolumab  |                                     |                                |                      |                                |                                    |
| Grade 3 lymphopenia or asymptomatic amylase or lipase  | 3                                   |                                |                      | None                           |                                    |
| Dosing-related  |                                     |                                |                      |                                |                                    |
| Any event that leads to delay in dosing lasting > 8 weeks from the previous dose requires discontinuation, with the exception of dosing delays to allow for prolonged steroid tapers to manage AEs. 
 
Dosing delays lasting > 8 weeks from the previous dose that occur for non-drug-related reasons may be allowed if approved by the study medical monitor/designee
 
 |                                     |                                |                      | Discontinue                    |                                    |

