Patients may resume treatment with IV study drug when the drug-related AE(s) improve to Grade ≤ 1 or resolve to baseline value, with the following exceptions which are allowed: Grade 2 fatigue, Grade 2 skin toxicity (if no Grade 3 drug related skin AE). For patients with Grade 2 AST, ALT, or total bilirubin elevations, dosing may resume when laboratory values return to baseline and management with corticosteroids, if needed, is complete. Drug-related pulmonary toxicity, diarrhea or colitis must have resolved to baseline before treatment is resumed. Patients with persistent Grade 1 pneumonitis after completion of a steroid taper over at least 1 month may be eligible for retreatment if discussed with and approved by the study medical monitor. Patients with drug-related endocrinopathies adequately controlled with only physiologic hormone replacement may resume treatment after consultation with the study medical monitor. Adrenal insufficiency requires discontinuation regardless of control with hormone replacement.

The patient may continue at same or reduced dose at the discretion of the investigator. If treatment is resumed at the same dose, and the patient experiences the same toxicity, treatment should be interrupted, then resumed at a reduced dose following improvement of the event to ≤ CTCAE Grade 2. If the patient continues to experience toxicity, additional dose reduction steps are permitted; however, the investigator should consult with the sponsor's medical monitor before reducing to 300 mg BID.

In most cases of Grade 3 ALT or AST elevation, IV study drug will be permanently discontinued. For patients with Grade 3 ALT or AST elevations after the start of IV dosing, but on a background of previous elevations on the first cycle of oral study drug, IV study drug hold is required, but discontinuation is not required, if ALT/AST elevations begin to resolve before the next scheduled infusion, and toxicity is considered to be mainly related to oral study treatment, after the investigator discusses the case with the study medical monitor. Levels will be monitored every 3 days; if they continue to rise more than 20%, the Hepatic Adverse Event Management Algorithm for a Grade 3 event will be followed. Treatment with IV drug may be resumed if levels return to Grade 2. If total bilirubin elevations > 2 × ULN accompany any of the ALT/AST elevations, IV drug should be discontinued.

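### Section 7.1.1 stops nivolumab permanently for immune-mediated encephalitis at any grade, but Table 4, the stated basis for re-treatment, allows it to restart after a Grade 2 event

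*Combined protocol and SAP*

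**What the plan says.** Section 7.1.1 (Immune-Mediated Encephalitis) has nivolumab withheld when moderate to severe neurologic signs or symptoms appear. If other causes are excluded, it prescribes corticosteroids followed by a taper, and it ends: "Permanently discontinue OPDIVO for immune-mediated encephalitis". No grade is attached.

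Dosing decisions are sent elsewhere. Section 5.2 says: "Please refer to Section 6 for guidance regarding Nivolumab schedule in response to toxicity". Section 6 says: "Dose modification and re-treatment of oral and/or IV study drug are to be based on criteria presented in Table 4".

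Four parts of Table 4 bear on nivolumab here:

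- **Grade 2, non-hematological and non-skin.** The row is "Adverse event, except fatigue". The action is Hold, with re-treatment at Grade 1 or below or baseline.
- **Grade 3 exception.** The row is "Uveitis, pneumonitis, bronchospasm, neurological toxicity, hypersensitivity reaction or infusion reaction of any duration". The action is Discontinue.
- **Footnote 3.** "Patients may resume treatment with IV study drug when the drug-related AE(s) improve to Grade ≤ 1 or resolve to baseline value". Listed conditions follow for liver tests, pulmonary toxicity, diarrhea or colitis, endocrinopathies and adrenal insufficiency. Encephalitis and neurological toxicity are not among them.
- **Footnote 2.** The investigator may stop nivolumab for any event judged a substantial risk. A patient on hold is to be re-evaluated at least weekly and to restart at the next dosing window once the re-treatment criteria are met.

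**The concern.** One section makes a permanent stop mandatory. The table that sites are told to use for re-treatment leaves the same decision to judgment when the event is Grade 2. A site working from Table 4 alone would not see the stop, because Section 6 never mentions encephalitis and does not refer back to Section 7.1.1. The protocol states no order of precedence between the two.

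At stake is re-exposure to nivolumab after an event for which Section 7.1.1 forbids it. Appendix C describes brain inflammation as possibly life threatening or fatal. This is a patient-safety instruction and does not touch the efficacy analysis.

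**Working it through.** The plan states no figure on this point, so the main check is a comparison of the two rules by grade.

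| Grade of encephalitis | Section 7.1.1 | Table 4 and footnotes (nivolumab) | Result |
|---|---|---|---|
| 2, first step | Withhold during work-up | Hold | Agree |
| 2, after recovery | Permanent stop | May resume at Grade 1 or below, or baseline | Conflict |
| 3 | Permanent stop | Discontinue (neurological toxicity) | Agree |
| 4 | Permanent stop | Discontinue (Grade 4 row) | Agree |

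No row of Table 4 is set at Grade 1, so it gives no opposing instruction there.

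**Is Grade 2 within the Section 7.1.1 stop?** The work-up starts at moderate signs, and other paragraphs of Section 7.1.1, such as pneumonitis and colitis, equate moderate with Grade 2. The infusion-reaction paragraph that follows limits its stop to severe or life-threatening events. The encephalitis paragraph has no such limit.

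**Does the 8-week delay rule catch the case?** Not reliably. Table 4 stops nivolumab after a delay of more than 8 weeks, but "with the exception of dosing delays to allow for prolonged steroid tapers to manage AEs". Section 7.1.1 prescribes a steroid taper for encephalitis. It gives no duration, so the exemption could apply but is not certain to.

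**Does footnote 3 ever carry an absolute stop?** Yes: "Adrenal insufficiency requires discontinuation regardless of control with hormone replacement". There is no counterpart for encephalitis.

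**How often could this arise?** Inputs: n = 36 (Section 11.1), and the Appendix C Rare band for brain inflammation, 0.01% to less than 0.1%, any grade. The band is assumed to apply to the combination and patients are treated as independent.

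Expected cases = n × p:

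- 36 × 0.0001 = 0.0036
- 36 × 0.001 = 0.036

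Chance of at least one case = 1 − (1 − p)^n:

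- 1 − (1 − 0.0001)^36 = 0.0036, about 0.4%
- 1 − (1 − 0.001)^36 = 0.0354, about 3.5%

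These are figures for all grades together. The documents do not give the Grade 2 share, so the chance that the conflict itself arises is lower by an unknown factor.

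**The case against.** The strongest reply is that the rule already exists and the specific should govern the general. Section 7.1.1 names the event, whereas Table 4 reaches it only through a catch-all row. The structure supports this reading. The paragraphs on pneumonitis, colitis, hepatitis, endocrinopathy, adrenal insufficiency and nephritis each refer to Section 6. The encephalitis and infusion-reaction paragraphs do not, and each states its own stop. In addition, footnote 3 only permits resumption, footnote 2 directs discontinuation where the investigator sees substantial risk, and Section 5.4 ends treatment for unacceptable adverse events. A physician who stops permanently complies with every section.

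Two further points are fair. The documents do not show how confirmed encephalitis would be graded, so the Grade 2 case is an assumption. The adrenal comparison is also weak, because Table 4 itself allows re-treatment after Grade 2 adrenal insufficiency despite the footnote sentence.

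These points limit the severity, but the conflict remains. Specific over general is a sensible reading that the protocol never states, and Section 7.1.1 is headed as a supportive care guideline while Section 6 is the dosing section. Permission to resume is still at odds with a prohibition. Footnote 2 also works in the other direction, since it has held patients restart once the criteria are met.

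**Conclusion.** The concern holds, as a minor inconsistency. Applied as written, Table 4 allows nivolumab to be given again after Grade 2 immune-mediated encephalitis, which Section 7.1.1 forbids. The conflict is confined to what follows a Grade 2 event, and Table 4 permits re-treatment without requiring it.

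The conclusion assumes that a confirmed case can be graded 2, which Section 7.1.1's own use of moderate supports but does not prove. The frequency range also assumes that the Appendix C band carries over to rucaparib plus nivolumab. The primary endpoint, the sample size of 36 and the planned analyses do not depend on this point.

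**What to change.** Make two wording changes in Section 6:

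1. Add a row to the Table 4 nivolumab exceptions: *Immune-mediated encephalitis, any grade: Discontinue*, with no re-treatment.
2. Add to footnote 3, beside the adrenal insufficiency sentence: *Immune-mediated encephalitis requires discontinuation at any grade; no re-treatment.*

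Both carry the existing Section 7.1.1 rule into the table that sites are told to use. The cost is one table row and one footnote sentence in a protocol amendment. There is no new clinical policy and no effect on data collection or analysis.

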### 7.1.2 Rucaparib

#### **Rucaparib Photosensitivity:**

Photosensitivity has been observed in patients treated with rucaparib. Patients should avoid spending time in direct sunlight because they burn more easily during treatment with rucaparib. When outdoors, patients should use typical precautions such as applying sunscreen (sun protection factor 50 or greater) and/or covering exposed skin with clothing and wearing a hat and sunglasses.

**Anticoagulants:** Rucaparib is a weak inhibitor of CYP2C9 in vivo. Use of Warfarin, Coumadin,

Tizanidine, and Aripiprazole is now an exclusion criterion for study eligibility.

